7.4. CLASSIFICATION OF RESPONDER STATUS

7.4.1. Classification as a responder

To be a 600 mg responder at the EXIT DBPCFC, a subject must meet both of the following conditions:

- 1) Must have attained an MTD \geq 600 mg of peanut protein on Exit DBPCFC
- 2) Must not have experienced more than mild symptoms through 600 mg of peanut protein on Exit DBPCFC.

Classification as a 300 mg, a 2000 mg, and a 1000 mg responder are defined similarly.

A 600 mg responder is equivalent to tolerating \geq 1043 mg cumulative of peanut protein during their Exit DBPCFC. Likewise a 443 mg cumulative corresponds to a 300 mg responder, a 2043 mg cumulative dose corresponds to 1000 mg responder, and 4043 mg cumulative corresponds to a 2000 mg responder.

Responders at maintenance DBPCFC for Group 1 subjects are defined similarly.

7.4.2. Classification as a non-responder

If a subject cannot be classified as a responder at a given dose level, then that subject should be classified as a non-responder at that dose level.

7.5. DATA DERIVATIONS AND DEFINITIONS

The following definitions and derivations will be used throughout this study:

- Study day is calculated relative to the first dose date in ARC004 as (assessment date – first dose date + 1) for assessments and visits performed on or after the first dose date, and (assessment date – first dose date) for assessments and visits prior to the first dose date.
- In this follow on study, baseline is defined as the last non-missing value prior to the first dose of study treatment in the study where study product is first received. For Group 1 patients (those previously on placebo in ARC003), baseline is relative to first dose of AR101 in study ARC004. For Group 2 patients (those continuing on AR101 therapy from ARC003), baseline is relative to first dose of AR101 in study ARC003. If no ARC004 data were entered for a Group 1 subject, use the last available ARC003 data prior to first dose of AR101 in ARC004. For food challenge end points, the ARC003 exit food challenge will serve as the baseline for both groups.

Sponsor: Aimmune Therapeutics, Inc.

Protocol: ARC0004

Version: Version 1.0, 10Jul2019

- Change from baseline is calculated as observed value after the first dose – baseline value.
- Group 1 Initial Dose Escalation period is defined as the time period beginning with the date and time of the first dose of study product in clinic and ending with the date of the last dose of study product taken prior to Up-dosing.
- Group 1 Up-dosing period is defined as the time period beginning with the date and time of the first home dose of study product at 3 mg, and ending with the date and time of first in-clinic dose at 300 mg. This period will be, ideally, 22 weeks in duration, but may be extended to a maximum of 40 weeks to accommodate dose reductions and re-escalations, if necessary.
- Group 1 Maintenance period is defined as the time period beginning with the date and time of the first home dose of study product at 300 mg and ending with the date of the last dose of study product taken prior to the maintenance DBPCFC. The maintenance period lasts approximately 24 weeks.
- Extended Maintenance (EM) period for Group 1 is defined as the time period beginning with the date and time of first dose of study product after the maintenance DBPCFC and ending with the date of the last dose of study product taken prior to Exit DBPCFC. Group 2 subjects will have undergone the Initial Dose Escalation, Up-dosing, and Maintenance Periods in ARC003 and will therefore enter the ARC004 EM period directly. The EM period for Group 2 is defined as the time period beginning with the date and time of first dose of study product in ARC004 and ending with the date of the last dose of study product taken prior to Exit DBPCFC. Length of EM period vary by group and cohort. See [section 2.3](#) for additional detail about each group and cohort.
- Exit DBPCFC period is defined as the time period beginning with the date and time of the first Exit DBPCFC dose and through 24 hours after the last dose of DBPCFC product.
- A DBPCFC is given in 2 parts, either on the same day, on consecutive days, or occasionally on non-consecutive days. For the non-consecutive days, the period of time more than 24 hours after the first part and before the second part begins will be attributed as follows
 1. For the Group 1 maintenance DBPCFC this is attributed to the Maintenance Period
 2. For the Exit DBPCFC Period it is attributed to the EM period.

Sponsor: Aimmune Therapeutics, Inc.

Protocol: ARC0004

Version: Version 1.0, 10Jul2019

- The active treatment period is defined as the time period beginning with the date and time of the first dose of study product in ARC004 and ending with the date and time of the last dose of study product in ACR004.
- Duration of active treatment period (days) is calculated as the date of last dose in ARC004 minus the date of first dose in ACR004 plus 1, excluding the DBPCFC periods.
- The Exit DBPCFC is defined as indeterminate if the subject was not able to tolerate the placebo challenge up to and including a dose of 2000 mg.

7.6. MISSING DATA

All AEs with partial/missing dates and times will be considered Treatment-Emergent Adverse Events (TEAEs) unless a partial date clearly indicates that it occurred prior to first dose of study treatment or more than 30 days after the last dose of treatment. All therapies with partial or missing dates and times recorded on the Concomitant Medication or Non-Drug Therapy CRF pages will be considered concomitant unless a partial stop date and time clearly indicates it was stopped prior to the first dose of study treatment. Start and stop dates will be imputed when partial dates are present as needed to determine treatment-emergent events and concomitant medications. No imputation will be done for a completely missing start/stop date or for subjects who did not receive study treatment.

Start dates with a missing day but which have month and year populated will be imputed such that:

- If the provided month and year match the month and year for that subject's first dose date, then the Day 1 date will be used
- In all other cases the 1st of the month will be used with the provided month and year

Start dates with a missing day and month but which have year populated will be imputed such that:

- If the provided year matches the year for that subject's first dose date, then the first dose date will be used
- In all other cases the 1st of January will be used with the provided year

Stop dates will be imputed as follows:

- Missing day with a provided year and month will use the last day of the month
- Missing day and month with provided year will use December 31

If the imputed stop date is greater than the last study date for the subject, then the imputed date will be replaced with the last known subject date.

Sponsor: Aimmune Therapeutics, Inc.

Protocol: ARC0004

Version: Version 1.0, 10Jul2019

The reported date of the most recent reaction to peanut on the peanut allergy history CRF page and date of diagnosis of peanut allergy will be imputed when the month or day is missing as follows:

- Missing day is set to 1 if the same year and month as the informed consent date. Otherwise it is set to 15
- Missing month and day are set to Jan 1 if the same year as the informed consent date. Otherwise it is set to July 1.

For any anaphylactic reactions that are missing severity, severe, the highest severity on the Muraro scale, will be imputed. For any allergic reactions that are missing severity, severe, the highest rating on the Consortium of Food Allergy Research (CoFAR) scale, will be imputed. For any other adverse events that are missing severity, severe, the highest rating on the Common Terminology Criteria for Adverse Events (CTCAE) scale, will be imputed.

No imputations will be made for other missing data, unless specified otherwise.

7.7. POOLING

In general for summaries of event data, Group 2 cohorts 3B and 3C will be combined and summarized together. For overall summaries of QD exposure in Group 2, the QD exposure period will be pooled across all Group 2 cohorts.

Sponsor: Aimmune Therapeutics, Inc.

Protocol: ARC0004

Version: Version 1.0, 10Jul2019

8. DEMOGRAPHIC, OTHER BASELINE CHARACTERISTICS

8.1. SUBJECT DISPOSITION AND WITHDRAWALS

The number of subjects enrolled as well as the number and percentage of subjects who entered each study period, and were included in each analysis population will be summarized by age group (ages 4-17, 18-55) and group/cohort (Group 1, Group 2 Cohort 1, Group 2 Cohort 2, Group 2 Cohort 3A, Group 2 Cohort 3B, Group 2 Cohort 3C, and Total).

Primary reason for early discontinuation from the study will be summarized as well as whether subjects underwent the exit DBPCFC.

Inclusion and exclusion eligibility will be listed separately.

8.2. PROTOCOL DEVIATIONS

All protocol deviations as defined in [Section 5](#) will be listed by subject. Major protocol deviations will be summarized for the Safety population for age group 4-17 years by group/cohort (Group 1, Group 2 Cohort 1, Group 2 Cohort 2, Group 2 Cohort 3A, Group 2 Cohort 3B, Group 2 Cohort 3C, and Total).

8.3. DEMOGRAPHIC AND OTHER BASELINE CHARACTERISTICS

Summary statistics for demographic and baseline characteristics will be provided for the Safety population summarized by age group (ages 4-17, 18-55) and group/cohort (Group 1, Group 2 Cohort 1, Group 2 Cohort 2, Group 2 Cohort 3A, Group 2 Cohort 3B, Group 2 Cohort 3C, and Total).

Demographic data will include age, sex, country, ethnicity, race, height, body weight, and body mass index (BMI). Baseline characteristics include total IgE, ps-IgE, ps-IgG4, ps-IgE/IgG4 ratio, SPT mean wheal diameter at screening, MTD of peanut protein at ARC003 Exit DBPCFC, childbearing potential, method of birth control, and history of asthma.

Demographic characteristics that cannot change over time (e.g., race) are summarized as collected in ARC003.

Age will be calculated relative to date of informed consent for the ARC004 study, as follows:

- If the month and day portion of the informed consent date is prior to the month and day portion of the birthdate, age will be calculated as the year of informed consent minus the year of birth, minus one;

Sponsor: Aimmune Therapeutics, Inc.

Protocol: ARC0004

Version: Version 1.0, 10Jul2019

- If the month and day portion of the informed consent date is on or after the month and day portion of the birthdate, age will be calculated as the year of informed consent minus the year of birth.

8.4. PEANUT ALLERGY HISTORY

The duration of peanut allergy (months since peanut allergy diagnosis), number of anaphylactic reactions to peanut in lifetime, months since most recent allergic reaction, and the symptoms experienced during the most recent peanut exposure will be summarized for the Safety population for age group 4 to 17 years by group/cohort (Group 1, Group 2 Cohort 1, Group 2 Cohort 2, Group 2 Cohort 3A, Group 2 Cohort 3B, Group 2 Cohort 3C, and Total).

For Group 2, peanut allergy history is taken as entered in the ARC003 CRF. For Group 1, peanut allergy history is taken as entered in the ARC004 CRF, except for date of first diagnosis of peanut allergy which is reported as collected in ARC003 because it does not change over time.

The reported date of the most recent allergic reaction and date of diagnosis of peanut allergy will be imputed based on the logic in [section 7.6](#).

Peanut allergy history will be listed for all subjects.

8.5. NONPEANUT ALLERGY HISTORY

Nonpeanut allergy history will be listed for all subjects. The presence of nonpeanut allergy history and type of allergy will also be summarized for the safety population for age group 4 to 17 years by group/cohort (Group 1, Group 2 Cohort 1, Group 2 Cohort 2, Group 2 Cohort 3A, Group 2 Cohort 3B, Group 2 Cohort 3C, and Total).

For Group 2, nonpeanut allergy history will be taken as entered in the CRF in ARC003. For Group 1, nonpeanut allergy history will be taken as entered in the CRF in ARC004.

8.6. OTHER MEDICAL HISTORY

Medical history will be listed for all subjects. Subjects with abnormal medical history events will be summarized for the safety population for age group 4 to 17 years by group/cohort (Group 1, Group 2 Cohort 1, Group 2 Cohort 2, Group 2 Cohort 3A, Group 2 Cohort 3B, Group 2 Cohort 3C, and Total) and by the Medical Dictionary for Regulatory Activities (MedDRA) system organ class (SOC) version 19.1 and preferred term (PT).

Medical history will be considered prior to the start of study product dosing. For Group 2, medical history will be taken as entered in the CRF in ARC003. For Group 1, medical history will be taken as entered in the CRF in ARC004.

9. EFFICACY

9.1. ANALYSIS OF EFFICACY SECONDARY ENDPOINTS

To confirm the efficacy of AR101 through reduction in clinical reactivity as measured in a DBPCFC to a cumulative dose of 4043 mg, the Exit food challenge will be summarized by group/cohort (Group 1, Group 2 Cohort 1, Group 2 Cohort 2, Group 2 Cohort 3A, Group 2 Cohort 3B, and Group 2 Cohort 3C). For Group 1, the maintenance DBPCFC will be summarized separately. Non-food-challenge efficacy endpoints also will be summarized by group/cohort (Group 1, Group 2 Cohort 1, Group 2 Cohort 2, Group 2 Cohort 3A, Group 2 Cohort 3B, and Group 2 Cohort 3C). Except where otherwise noted, DBPCFC summaries will be included for the completer population for age group 4-17 years.

The study examines DBPCFC changes from the baseline of study ARC004 (i.e. DBPCFC completed at end of study ARC003) to the end of study ARC004.

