Throughout ARC004 EM, the first 2 doses at extended nondaily dosing intervals (BIW, QW, QOW) will always be administered under direct supervision in the clinic; QOD dosing is an exception and can be initiated at home. Thereafter, the doses will be administered at home as tolerated, and recorded in the subject diary. Investigators may, at their discretion, bring subjects back to the research unit for an observed dose at any time. All AR101 doses will be judged by the investigator to be tolerated or not tolerated according to criteria previously established in ARC003 and specified in [Section 6.5.2](#).

Dosing intervals should be as consistent as possible, preferably on the same days each week.

- In the BIW group, doses should be at least 3 days apart (eg. Monday and Thursday each week)
- In the QW group, doses should be taken on the same day (\pm 1 day) each week
- In the QOW group, doses should again be taken on the same day (\pm 2 days), every other week

Any subject receiving nondaily dosing (QOD, BIW, QW, or QOW) who has 1 related SAE; 1 related AE graded severe; 2 related AEs occurring on separate occasions, both graded moderate; or 3 consecutive doses judged “not tolerated,” will be considered a treatment failure in the statistical analysis of each cohort. These subjects will be returned to a 300-mg daily regimen by entering the Repeat Up-dosing period. For the majority of subjects, Repeat Up-dosing will be carried out in Treatment Pathway 2 of ARC008. However, if ARC008 is not available at the study site, subjects may start AR101 daily dosing and have visits in ARC004 until ARC008 is available, then continue dosing in ARC008.

No subject will be exposed to a longer dosing interval if evidence from previous cohorts suggests that doing so would more likely than not cause the subject to either experience more frequent or more severe AEs, or lose desensitization that he or she may have gained/maintained, compared to more frequent dosing. Because subjects in Cohorts 3B and 3C will have had 28 additional weeks of QD maintenance treatment, these subjects will be allowed to proceed to QOD and BIW dosing independent of Cohort 2’s experience according to the judgment of the Safety Monitoring Committee (SMC).

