Aimmune will monitor the safety and efficacy in each of the cohorts in accordance with internal procedures and escalate to the internal Safety Monitoring Committee (SMC) for review and recommendation for action. Only when sufficient efficacy and safety evidence is available on a cohort, will the SMC recommend that the next cohort advance to a longer interval between doses. Therefore, only after the safety and efficacy data from Group 2 cohorts are available, reviewed, and approved by the SMC, will the SMC allow the Group 1 patients to modify their once-daily regimen.

For more information on individual-, cohort-, and study-stopping rules, see [Section 7.8](#).

Down-dosing may be necessary during the Extended Maintenance Period due to safety or tolerability reasons; however subjects who had to be down-dosed remain in the Extended Maintenance Period during the dose adjustment. The duration of the Extended Maintenance Period does not reset if this occurs.

Early Discontinuations

Subjects who are discontinued and who do not enter ARC008 will be followed for safety for a minimum of 30 days after the last dose of AR101, 2 weeks after the last food challenge, or until resolution or stabilization of all AEs ongoing at the time dosing is stopped, whichever is longer. In addition, subjects who are discontinued from further AR101 dosing due to chronic or recurrent GI AEs will have experienced an AE of interest (AEI) and will be followed monthly for a minimum of 6 months, or until resolution or stabilization of all GI AEs ([Section 7.3.3.2](#) for more information about GI AEIs).

For subjects who do not tolerate their nondaily dosing regimen and subjects who switch to daily dosing after missing their nondaily dose for > 3 days, the exit DBPCFC will be omitted before discontinuation from ARC004 and enrollment in ARC008.

Subjects who are discontinued will not be replaced.

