6.3.7 Double-Blind, Placebo-Controlled Food Challenge (Groups 1 and 2)

Group 1 subjects will undergo a Post-Maintenance DBPCFC, to be conducted in the same manner as the ARC003 Exit DBPCFC, but with a top dose of 2000 mg (4043 mg cumulative) peanut protein added, as shown in [Table 4](#).

All subjects in Groups 1 and 2 who complete their dosing regimen will undergo an Exit DBPCFC up to a single highest dose of 2000 mg of peanut protein (4043 mg cumulative), according to [Table 4](#). For subjects who do not tolerate their nondaily dosing regimen and subjects who switch to daily dosing after missing their nondaily dose for > 3 days, the Exit DBPCFC will be omitted before discontinuation from ARC004 and enrollment in ARC008. Subjects should not administer their AR101 dose on the day of the DBPCFC. All DBPCFCs will be conducted and evaluated based on PRACTALL guidelines. Sites will be provided a DBPFCFC manual, as in ARC003.

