7.8.3 Cohort Stopping Rules

ARC004 will consecutively enroll eligible subjects into different cohorts, each of which will produce evidence during the trial concerning the feasibility and safety of adjusting EM dosing from daily to a less frequent schedule. The information that becomes available as each cohort proceeds through the study will be evaluated before determining whether the next cohort is to advance to a longer interval between doses. No subject will be exposed to a regimen with longer dosing intervals (eg, QOD to BIW, BIW to QW, or QW to QOW) if evidence from the previous cohorts suggests that doing so would more likely than not cause subjects at the new interval to either experience more frequent or more severe AEs, or lose desensitization that they may have gained/maintained, had they remained on more frequent dosing. Because they will have had 28 additional weeks of QD maintenance, Cohorts 3B and 3C will be allowed to proceed to QOD and BIW dosing independent of Cohort 2's experience according to the judgment of the Safety Monitoring Committee (SMC).

For each cohort, all subjects discontinuing early due to AEs (eg, dropouts) will be considered failures. Likewise, subjects who lose protection during their ARC004 Exit DBPCFC, when compared either to their ARC003 Exit DBPCFC (Group 2), or their ARC004 Post-Maintenance DBPCFC (Group 1) will be considered failures (eg, failed completers), as follows:

- Subjects tolerating 443 mg at the previous DBPCFC must tolerate ≥ 443 mg at the ARC004 Exit DBPCFC, or be considered a failure
- Subjects tolerating 1043 mg at the previous DBPCFC must tolerate ≥ 443 mg at the ARC004 Exit DBPCFC, or be considered a failure
- Subjects tolerating 2043 mg (or greater, for Group 1 subjects) at the previous DBPCFC must tolerate ≥ 1043 mg at the ARC004 Exit DBPCFC, or be considered a treatment failure

The treatment failure rate in each cohort will be monitored on an ongoing basis by the SMC, and calculated according to the following formula:

Treatment failure rate = [(dropouts) + (failed completers)] / planned size* for the cohort

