3.2. SECONDARY ENDPOINTS

The secondary safety endpoints are as follows:

- Frequency of anaphylactic reaction
- Frequency of use of epinephrine as a rescue medication
- Frequency of AEs leading to withdrawal of AR101
- Frequency of AEs in each treatment regimen leading to discontinuation of extended interval dosing
- Frequency of Gastrointestinal (GI) AEIs
- Occurrence of premature discontinuation of dosing due to chronic/recurrent gastrointestinal (GI) AEs
- Frequency of accidental food allergen exposure
- In subjects with asthma, change in asthma control using the Asthma Control Test (ACT) questionnaire
- Frequency of all above safety endpoints by treatment period

The secondary efficacy endpoints are as follows:

- The proportion of subjects in each regimen tolerating a single dose of 600 mg (≥ 1043 mg cumulative) of peanut protein during their Exit DBPCFC
- The proportion of subjects in each regimen who tolerate a single dose of 300 mg (≥ 443 mg cumulative) of peanut protein during their Exit DBPCFC
- The proportion of subjects in each regimen who tolerate a single dose of 2000 mg (4043 mg cumulative) of peanut protein during their Exit DBPCFC
- Maximum tolerated dose and change from baseline* at the Maintenance DBPCFC** and each Exit DBPCFC
- Maximum severity of symptoms at each challenge dose at the Maintenance DBPCFC** and each Exit DBPCFC

Sponsor: Aimmune Therapeutics, Inc.

Protocol: ARC0004

Version: Version 1.0, 10Jul2019

- Frequency of use of epinephrine as a rescue medication at the Maintenance DBPCFC** and each Exit DBPCFC
- Change in QoL as assessed by the food allergy related quality of life questionnaire (FAQLQ) and the food allergy independent measure (FAIM) questionnaires
- Satisfaction with AR101 treatment as assessed by the TSMQ-9 questionnaire and additional questions
- Changes in peanut-specific (ps) serum immunoglobulin E (IgE) and IgG4 levels
- Changes in peanut skin prick test (SPT) wheal diameter

*Baseline is defined as the Exit DBPCFC from ARC003 for both treatment groups.

**Maintenance DBPCFC is defined only for Group 1.

Sponsor: Aimmune Therapeutics, Inc.

Protocol: ARC0004

Version: Version 1.0, 10Jul2019

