4.1. SAFETY POPULATION

The primary population of analysis for all analyses will be the Safety population. The Safety population will consist of all subjects who receive at least one dose of study treatment during ARC004.

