4.2. COMPLETER POPULATION

The Completer population will include all subjects in the safety population who have at least one evaluable maintenance or exit DBPCFC, where an evaluable DBPCFC is defined as completion of at least the peanut part of the food challenge.

Sponsor: Aimmune Therapeutics, Inc.

Protocol: ARC0004

Version: Version 1.0, 10Jul2019

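### Exit food-challenge response rates are planned in completers, so nondaily treatment failures who are never challenged drop out of the Cohort 2, 3B and 3C rates

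*SAP*

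**What the plan says.** **Population.** SAP 9.1 states: "Except where otherwise noted, DBPCFC summaries will be included for the completer population", and limits this to ages 4-17. SAP 9.1.1 plans Exit response rates with exact Clopper-Pearson intervals for each group/cohort. It names no other population, so the default applies. SAP 4.2 admits Safety subjects who "have at least one evaluable maintenance or exit DBPCFC". A note to SAP 3.2 adds: "Maintenance DBPCFC is defined only for Group 1".

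**Stated primary population.** SAP 4.1 reads: "The primary population of analysis for all analyses will be the Safety population". Protocol 9.1 says the same. SAP 11 lists three exceptions to the protocol's analyses. All concern the challenge baseline or the reporting and naming of the maintenance challenge; none is the completer restriction.

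**Who is challenged.** Under Protocol 3.1.5, a nondaily subject who meets the related-AE or not-tolerated-dose criteria "will be considered a treatment failure in the statistical analysis of each cohort". The same section says that, for subjects who do not tolerate their nondaily regimen and for those who switch to daily dosing after missing doses for more than 3 days, "the exit DBPCFC will be omitted before discontinuation from ARC004 and enrollment in ARC008". Protocol 6.3.7 repeats this. Protocol 3 ties intolerance of the nondaily regimen to Section 7.8.2, which lists the same failure criteria.

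**The concern.** Protocol 1.3 gives the aim: to learn whether intermittent dosing can preserve the desensitization gained by daily dosing. Protocol 9.2.2 words the efficacy endpoints as proportions of subjects in each regimen. With no hypothesis tests, the per-cohort response rates and their intervals carry the efficacy message.

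A rate among completers describes only subjects who stayed on the regimen long enough to be challenged. A subject whom the protocol calls a treatment failure on twice-weekly dosing does not lower the twice-weekly response rate; the subject disappears from it. A reader who takes the table as the chance of responding when assigned to that regimen would be misled in the favourable direction.

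**Working it through.** **Which subjects are excluded**

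1. SAP 9.1 and 9.1.1: Exit response rates use the Completer population.
2. SAP 4.2 and 3.2: the maintenance challenge exists only for Group 1, so a Cohort 2, 3B or 3C subject is a completer only with an evaluable Exit challenge.
3. Protocol 3.1.5 and 6.3.7: the Exit challenge is omitted for nondaily intolerance.
4. Protocol 3.1.5: those meeting the nondaily criteria are treatment failures in the cohort analysis.

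Subjects in step 4 are therefore outside the set in step 1.

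**Plan's own figure.** The plan gives no figure for this point. The only ARC004 design figure is an 80% probability of seeing at least one AE with about 400 subjects at 4 per 1,000. It reproduces (1 - 0.996^400 = 0.799), but nothing here depends on it.

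**Formula.** Let C be the subjects challenged, F those unchallenged, and x the responders. The completer rate is x/C. The all-treated rate, with the unchallenged as non-responders, is x/(C+F). The gap is x/C - x/(C+F) = (x/C) × F/(C+F).

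**Inputs.** Cohort 2 size 50 and Cohort 3 size 175, so 175/3, about 58 per arm (Protocol 7.8.3). These are planned sizes for all ages, whereas the SAP table covers ages 4-17. Response among the challenged is assumed to be near the ARC002 post-plateau results on daily dosing: 100%, 90% and 60% at 443, 1043 and 2043 mg cumulative (Protocol 1.2.2), which correspond to 300, 600 and 1000 mg single doses. The numbers unchallenged are assumptions.

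**Cohort 2, 600 mg (95% Clopper-Pearson)**

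| Unchallenged | Completers | All treated | Gap (points) |
|---|---|---|---|
| 5 | 40/45 = 88.9% (75.9-96.3) | 40/50 = 80.0% (66.3-90.0) | 8.9 |
| 10 | 36/40 = 90.0% (76.3-97.2) | 36/50 = 72.0% (57.5-83.8) | 18.0 |
| 15 | 32/35 = 91.4% (76.9-98.2) | 32/50 = 64.0% (49.2-77.1) | 27.4 |

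Formula check for 10 unchallenged: 0.90 × 10/50 = 0.18.

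**Other dose levels, 10 unchallenged.** At 300 mg, 40/40 = 100% against 40/50 = 80%, gap 20. At 1000 mg, 24/40 = 60% against 24/50 = 48%, gap 12. The gap is largest where response among the challenged is highest.

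**Cohort 3B or 3C, 600 mg, 12 of 58 unchallenged.** 41/46 = 89.1% against 41/58 = 70.7%, gap 18.4.

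**Range.** With 5% to 40% unchallenged and 70% to 90% response among completers, the gap runs from about 3 to 36 points.

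**Mechanism in the protocol's own data.** ARC001 (Protocol 1.2.1) had 23/29 = 79% in its intent-to-treat set and 23/23 = 100% in completers. Those were new starters, so this shows the mechanism and does not forecast Group 2.

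**The case against.** **The endpoint may be conditional.** Protocol 9.2.2 counts subjects who tolerate a dose during their Exit challenge, and Protocol 9.1 foresees a possible population limited to subjects who undergo it and allows further populations in the SAP. This stands as a reason to keep the completer table. It does not explain why Safety is named primary for all analyses and then not used here.

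**The non-responder rules may already cover it.** SAP 7.4.2 and 9.1.1 make anyone who is not a responder a non-responder. They name no population, so the completer default still does the excluding. A reader might instead blame the non-missing denominator in SAP 6.1, but that applies only unless specified otherwise and is not needed for the point. Table shells are in a separate document, so the outputs could differ; the SAP text as written is in conflict with itself.

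**The losses are visible elsewhere.** They are: SAP 8.1 shows by cohort who underwent the Exit challenge, SAP 10.3 tabulates AEs leading to withdrawal, and one secondary endpoint counts AEs that end extended-interval dosing. A reader could rebuild an all-treated rate by hand. The planned rates and intervals still omit these subjects.

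**A tempting stronger reading** is that the protocol already requires AE discontinuations to count as non-responders, because Section 7.8.3 says "all subjects discontinuing early due to AEs (eg, dropouts) will be considered failures". The documents do not support this. That text belongs to a cohort stopping rule. Its denominator is planned cohort size, and its criterion for completers is loss of protection against the previous challenge, not a fixed dose. The synopsis also limits the failure to related AEs. It should not be used to justify the scoring.

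**Stakes are limited.** The study is open-label and exploratory, intervals are descriptive, and the primary endpoint is treatment-related AEs. All of this stands.

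**Conclusion.** The point holds. As written, the SAP reports Exit response in completers although both documents name Safety as primary, and SAP 11 does not disclose the change. In Cohorts 2, 3B and 3C this removes subjects whom the protocol calls treatment failures, so the planned rates overstate the proportion responding on the assigned regimen.

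The size in ARC004 is unknown. The 18-point gap for Cohort 2 assumes 10 of 50 unchallenged, ARC002-like response among the challenged and the all-age planned size.

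A reader might infer that the tables are tilted towards nondaily dosing. That is not established. Under Protocol 6.3.10 the Early Discontinuation Visit has no food challenge, so daily-dosing discontinuers also leave the denominator. The nondaily cohorts have extra failure rules, so the bias can differ by regimen, but the documents do not show that it does. Nor is the completer rate wrong in itself: it answers a narrower question, conditional on being challenged.

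This is a cheap improvement to a secondary analysis. The primary endpoint is untouched.

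**What to change.** In SAP 9.1 and 9.1.1:

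- Add Exit response rates at 300, 600, 1000 and 2000 mg by assigned cohort in the Safety population, ages 4-17 as in 9.1. Put every treated subject in the denominator and score every subject without an evaluable Exit challenge as a non-responder under SAP 7.4.2.
- Show the unchallenged per cohort by reason: nondaily treatment failure, other AE discontinuation, missed-dose switch, other. The protocol does not call missed-dose switchers treatment failures, so they should be visible separately.
- Keep the completer table beside it, labelled as the rate conditional on being challenged.
- State the Group 1 Exit denominator. A Group 1 subject with a maintenance but no Exit challenge is a completer under SAP 4.2, and the SAP does not say whether that subject counts in the Exit rate.
- List the completer restriction in SAP 11 and reconcile 4.1 with 9.1.

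**Cost.** SAP wording and one more table set from data already collected; no change to trial conduct. The reported rates become less favourable. The all-treated rate also combines tolerability of the regimen with desensitization, which is why both tables are needed.
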